5.4.2 Methods of sample collection

The time interval for blood sample collection relative to the most recent intake of trial medication should be between 22 and 26 h. For quantification of empagliflozin trough plasma concentrations, 3 mL of blood will be drawn from a forearm vein in an EDTA-anticoagulant blood drawing tube at each time-point. Details of sample handling and sample logistics can be found in the ISF (Central lab manual).

5.4.3 Analytical determinations

Empagliflozin concentrations in plasma samples will be determined by a validated HPLC MS/MS assay (high performance liquid chromatography, tandem mass spectrometry). In order to identify samples from patients taking placebo, the bioanalyst will be un-blinded so that samples from patients receiving placebo will not be analysed for empagliflozin.

5.5 ASSESSMENT OF BIOMARKERS

Samples for NT-proBNP will be collected at Visit 1 (Screening) to determine whether the patient is eligible for the trial. Further samples for NT-proBNP will be collected at later time points in the trial (see [Flow Chart](#)) to investigate a potential effect of the trial medication. Samples for NT-proBNP will be analysed at the Central Laboratory.

Samples for the determination of high-sensitivity cardiac troponin T will be collected at Visit 2 (Randomisation) and analysed at the Central Laboratory.

5.5.1 Biobanking (optional)

Participation in sampling for biobanking (including DNA) is voluntary and not a prerequisite for participation in the trial. Biobanking samples will be taken only after separate informed consent has been given in accordance with local ethical and regulatory requirements. Banked samples may be analysed in the future for scientific evaluations or to further, for example, the mechanistic understanding of drug effects and/or to identify genetic or other factors associated with response to therapy or the risk of adverse drug reactions.

Proprietary confidential information © 2019 Boehringer Ingelheim International GmbH or one or more of its affiliated companies

Measures are in place to comply with the applicable rules for the collection, biobanking and future use of biological samples and clinical data, in particular.

- Sample and data usage has to be in accordance with the separate biobanking ICF.
- The BI-internal facilities storing biological samples from clinical trial participants as well as the external banking facility are qualified for the storage of biological samples collected in clinical trials
- An appropriate sample and data management system, incl. audit trail for clinical data and samples to identify and destroy such samples according to ICF is in place
- A fit for the purpose documentation (biomarker proposal, analysis plan and report) ensures compliant usage
- A fit for purpose approach will be used for assay/equipment validation depending on the intended use of the biomarker data
- Samples and/or data may be transferred to third parties and other countries as specified in the biobanking ICF

5.5.1.1 Methods and timing of sample collection

Sampling will be performed at the time points specified in the [Flow chart](#).

DNA banking

Approx. 8.5 mL blood will be drawn into a PAXgene Blood DNA Tube, preferably at Visit 2. In Korea, a 6 mL K2 EDTA tube will be used.

Plasma banking

Approx. 10 mL blood will be drawn into an EDTA blood collection tube.

Serum banking

Approx. 8.5mL blood will be drawn into a serum separation tube.

Urine banking

Approx. 10 mL urine (preferably morning mid-stream urine) will be collected.

For all biological samples collected, detailed instructions on sampling, preparation, processing, shipment and storage are provided in the laboratory manual. Plasma, serum and urine samples will be stored at an external biobanking facility contracted by the Sponsor; DNA, extracted from the original whole blood sample, will be stored at the Sponsor except for samples collected in China. These samples will be stored at an external biobanking facility contracted by the Sponsor.

5.6 OTHER ASSESSMENTS

5.6.1 EQ-5D

Health related quality of life will be assessed using the EQ-5D-5L version (refer [Appendix 10.2.1](#)) according to the [Flow Chart](#). EQ-5D is a standardised instrument for use as a measure of health outcome. It is designed for self-completion by patients.

The EQ-5D self-report questionnaire (EQ-5D) essentially consists of 2 pages comprising:

- the descriptive system (five dimensions of health; namely mobility, self-care, usual activities, pain/discomfort, anxiety/depression). Each dimension comprises five levels (no problems, slight problems, moderate problems, severe problems, extreme problems/unable to perform activity).
- the EQ-VAS (visual analogue scale) which records the patient's self-rated health status on a vertical graduated (0 – 100) VAS.

For further description on completing the questionnaire refer to the last part of [Section 5.2.1](#).

5.6.2 Health Care Resource Utilisation (HCRU)

HCRU data will be used for health economic analysis (i.e. cost-effectiveness analysis) required for reimbursement decisions. Resource use will be captured via interview with the patient and entered in the eCRF at all on-site visits during the complete trial period, and will allow calculation of direct and indirect costs. Main components to be collected are unscheduled outpatient visits and hospitalisations.

5.7 APPROPRIATENESS OF MEASUREMENTS

All measurements performed during this trial are standard measurements and will be performed in order to monitor safety aspects, and to determine empagliflozin efficacy and safety in an appropriate way.

The scheduled measurements are appropriate to see drug induced changes in vital signs, standard laboratory values, biomarkers specific to efficacy of treatment of HF, and ECG. The primary and secondary endpoints are accepted for evaluation of efficacy, safety and tolerability on an oral HF drug and they are widely used in respective pivotal phase III studies.

Health related quality of life questionnaires are a necessary part for this phase III trial in order to collect data for a health economic evaluation.

Therefore, the appropriateness of all measurements applied in this trial is given.

6 INVESTIGATIONAL PLAN

6.1 VISIT SCHEDULE

All trial visits, except for screening visit and telephone visits should preferably take place before noon. The patient should be fasting (no food or liquid except water the last 10 – 16 hours) at Visit 2 (Randomisation), EOT Visit and Follow Up Visit.

If a patient mistakenly takes trial medication on the morning of Visit 4 before attending the clinic or comes in non-fasted where a fasting condition is required (refer to the [Flow Chart](#)), the visit should be rescheduled for another day as soon as possible, reminding the patients about expected time of dosing. The rescheduled visit must take place in a short enough time-frame so that the patient has sufficient trial medication available.

All patients are to adhere to the visit schedule as specified in the [Flow Chart](#). If any visit has to be rescheduled, subsequent visits should follow the original visit date schedule. The trial medication packs contain sufficient medication to allow for these time windows.

6.2 DETAILS OF TRIAL PROCEDURES AT SELECTED VISITS

The [Flow Chart](#) summarises the investigational procedures to be done at each visit, and trial procedures should be performed before intake of any trial medication. The procedures are further described below.

6.2.1 Screening

No trial procedures should be done unless the patient has consented to taking part in the trial. Preferably the patient should also be informed about biobanking (including DNA) sampling already at this visit.

Patients who have been diagnosed with T1DM are to be provided with the consent form that contains information relevant for patients with T1DM.

Once the patient has consented to the trial participation, she/he is considered to be enrolled in the trial and have started screening. The patient should be registered in the enrolment log and be registered in the IRT as a screened patient. Patients will continue to take background medication for heart failure and treatment for their concomitant disorders if applicable. The screening visit may be conducted over multiple days, at the discretion of the investigator, as long as all screening procedures are performed and resulted within the allowable visit window in the [flow chart](#). For example, a site may obtain written informed consent followed by collection of samples for the safety lab analysis and ECG. Remaining procedures may be performed on a separate day, once it is confirmed that the patient's laboratory values, including NTproBNP value, are not exclusionary.

If the patient meets the entry criteria, Visit 2 should occur as soon as possible once it has been confirmed that the patient is eligible to continue. If the patient does not meet the entry criteria, the site may make a phone contact to inform the patient that he/she is no longer required to return to the clinic for Visit 2.

Patients who fail screening (fail to meet one or more of the inclusion criteria, and/or meet one or more of the exclusion criteria) following Visit 1 procedures should be registered as a screen failure in IRT.

6.2.2 Treatment period

Randomisation will occur at Visit 2 using IRT. The patients will return to the clinic for regularly scheduled visits 4, 12, 32 and 52 weeks after randomisation during the first year of trial participation, and every 24 weeks thereafter for the duration of the trial, as specified in the [Flow chart](#). These on-site visits will assess the occurrence of safety and efficacy endpoints, trial medication compliance, concomitant therapy or intervention.

Telephone follow-up calls will be scheduled 10-12 weeks after every on-site visit starting after Visit 4 and continuing throughout the trial (see [Flow chart](#)). The telephone contacts will focus on safety (e.g. hospitalisations or occurrence of AEs), changes in concomitant therapy and trial medication compliance.

The patients should be fasting at the Randomisation Visit.

Consenting patients with T1DM are to be provided with the ketone monitoring device, the patient diary and Trial information card. The site staff are to provide instruction to the patient on how to properly use the ketone monitoring device and the importance of recording their glucose, ketone and insulin intake throughout the trial. At all subsequent visits, site staff are required to review the patient's diary with the patient to ensure that the diary is properly completed. Patients with T1DM should be provided with ketone monitoring supplies as necessary.

The optional blood sample for DNA will preferably be collected at the Randomisation Visit for all patients eligible for randomisation, but could also be taken at any later visit after the separate consent is signed.

At any time during the treatment period the Investigator is allowed to adjust and optimise HF background therapy according to local and international guidelines.

If any additional therapy is considered necessary for the patient's welfare during the treatment period it may be given at the discretion of the Investigator (see also restrictions in [Section 4.2.2](#)).

For sites selected to participate in collection of samples for PK analysis, please refer to [Section 5.4](#) and the Lab Manual for details.

Patients will be dispensed medication at each on-site visit and allocation of new kit number(s) will be managed through the IRT. Trial medication administration should be done after physical and laboratory assessments.

This is an event driven trial. Patients will remain in the treatment period until the necessary number of events is reached.

Permanent trial medication discontinuation is only justified when clear persistent contraindications arise, or when the patient requests to stop trial medication. [See Section 6.2.4](#) for details on how to handle trial medication discontinuations, and [Section 3.3.4](#) for when discontinuation from trial is justified.

6.2.3 End of Treatment, Follow Up Period and Trial Completion

Patients on treatment at the time when required number of outcome events are reached (ref. [Section 7.7](#)), will be asked to return to the clinic for the EOT visit, with the proposed time schedule communicated via an investigator letter, followed by the Follow Up Visit 30 days later. If a patient has prematurely discontinued trial medication is not willing to return to the clinic for predefined trial visits, a telephone call at trial end will be required, to document the occurrence of outcome events and vital status. Other AEs and concomitant therapy changes since the last visit should be recorded in the eCRF. Sites should encourage the patient to return to the clinic for the final study visit (ref. [Section 3.3.4.1](#)).

During the EOT visit all trial medication will be collected and compliance calculated, occurrence of safety and efficacy endpoints will be assessed and complete physical examination, laboratory assessments and ECG will be performed (ref. [Flow Chart](#)).

The Follow Up Visit should also be a clinic visit for all patients, and the following examinations should be performed (ref. [Flow Chart](#)):

- Concomitant Therapy
- Vital signs and body weight
- NYHA classification
- Documentation of any adverse events and endpoints
- Vital status
- Blood and urinary sampling
- KCCQ and EQ-5D
- Modified Rankin Scale (only in case of suspected stroke within last 90 days)

6.2.4 The patients should be fasting at the EOT and Follow Up Visit. Early discontinuation of trial medication and trial termination

The EOT activities will be performed when a patient discontinues trial medication treatment permanently.

Note. The EOT activities should not be used for temporary interruptions of trial medication.

All patients will have a follow up visit 30 days following discontinuation of trial medication, irrespective whether they complete the treatment period or prematurely discontinue trial medication.

Patients who discontinue trial medication prematurely should thereafter continue to follow scheduled visits until trial end. For patients reluctant to attend the scheduled visits after prematurely discontinuing trial medication, some trial assessments may be negotiated with exception of collection of adverse events, outcome events and concomitant therapy.

Proprietary confidential information © 2019 Boehringer Ingelheim International GmbH or one or more of its affiliated companies

Please refer to [Section 3.3.4.1](#) for detailed procedures to be followed in case a patient wants to stop trial medication.

In case of early trial termination (e.g. based on recommendation by the DMC, a reasonable timeframe to stop the trial (perform last patient visits) will be defined and communicated to the Investigators.

7 STATISTICAL METHODS AND DETERMINATION OF SAMPLE SIZE

7.1 STATISTICAL DESIGN – MODEL

The eligible patients for this trial will be randomised to empagliflozin 10 mg and placebo in 1:1 ratio, stratified by geographical region, status of DM (DM, pre-DM, no DM), LVEF (<50%, ≥50%) and eGFR (CKD-EPI)_{cr} (<60 mL/min/1.73 m², ≥60 mL/min/1.73 m²) at screening visit.

To ensure the trial population consist of a reasonable combination of non-, pre- and DM patients, and to aim for approximately 35% to 50% of the population or more with an LVEF ≥50% capping will be used on trial level (see also [Section 3.3](#)). Capping on regional level may be applied to achieve a contribution of each region to each category of diabetes status.

The composite primary endpoint is the time to first event of adjudicated CV death or adjudicated HHF. The statistical model for the primary analysis is the Cox proportional hazards model. The hazard ratio and its confidence limits will be determined for evaluating the superiority of empagliflozin to placebo for the primary endpoint.

The key secondary endpoints, which are part of the testing strategy, are

- occurrence of adjudicated HHF (first and recurrent), and
- eGFR (CKD-EPI)_{cr} slope of change from baseline

7.2 NULL AND ALTERNATIVE HYPOTHESES

A hierarchical testing procedure will be followed for the assessment of the primary and the key secondary endpoints. For all endpoints, superiority of empagliflozin vs. placebo will be evaluated with a two-sided test in the following structure:

Null hypothesis: There is no difference between the effect of placebo and the effect of empagliflozin in terms of the endpoint in question.

Alternative hypothesis: There is a difference between the effect of placebo and the effect of empagliflozin in terms of the endpoint in question. The tests will be performed in the following hierarchical order:

1. Time to first event of adjudicated CV death or adjudicated HHF
2. Occurrence of adjudicated HHF (first and recurrent)
3. eGFR (CKD-EPI)_{cr} slope of change from baseline

Starting from step 1, if the null hypothesis is rejected, and the result is more favourable for empagliflozin, superiority is concluded in the tested endpoint, and the overall type I error is preserved for the test in the next step. If at any step the null hypothesis is not rejected, subsequent tests are conducted in an exploratory fashion.

Proprietary confidential information © 2019 Boehringer Ingelheim International GmbH or one or more of its affiliated companies

The overall type one error rate will be preserved at a level of 0.05 (2-sided). The type one error rate used at the final analysis will be influenced by the pre-planned interim analysis – see [Section 7.4](#).

In the final analysis after the evaluation of recurrent HHF, alpha will be split into 0.001 to be used for the analysis of eGFR slope, and the rest will be transferred to the meta-analyses.

In case the trial is finished early at the time of interim analysis, using $\alpha_{interim}$ for the primary and key-secondary endpoints in the testing hierarchy according to the α -spending function in [Section 7.4](#), the following α -split will be used for eGFR slope analysis and the meta-analyses:

- 0.1 * $\alpha_{interim}$ will be used for the eGFR slope analysis and
- 0.9 * $\alpha_{interim}$ will be transferred to the meta-analyses

In both the interim and final analyses, if the slope analysis is successful, the alpha of this branch will then be transferred to the meta-analyses.

The testing hierarchy is summarised in Figure 7.2: 1 showing the alpha-spending at the final analysis.

[figure not shown]

Figure 7.2: 1 Hierarchical analysis of trial in HFpEF (1245.110) and the parallel trial in HFrEF (1245.121) showing the alpha-spending at the final analysis.

The other secondary endpoints will be evaluated in an exploratory manner.

7.3 PLANNED ANALYSES

The primary efficacy analysis will be based on the randomised set (RS), including all randomised patients.

The safety analysis will be based on the treated set (TS), which consists of all patients treated with at least one dose of the trial medication.

For both efficacy and safety analyses, treatment will be evaluated as randomised.

For serum creatinine and values based on upon this measurement such as eGFR, baseline will be defined as the mean of all available measurements from the screening visit until start of randomised trial medication.

Baseline status of DM is defined as:

- DM: any pre-treatment HbA1c above 6.5 or history of DM as entered in the eCRF on the medical history page
- Pre-DM: no history of DM and no HbA1c ≥ 6.5 before treatment and a pre-treatment HbA1c value of ≥ 5.7 and < 6.5
- Non-DM: not meeting criteria of DM or pre-DM above

For all other endpoints, baseline will be defined as the last available measurement before start of randomised trial medication.

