Since there is a chance that empagliflozin, as a diabetes drug, when used in CV outcome trials recruits more patients with T2DM, capping on trial level will be used to aim for a similar distribution of patients with DM, pre-DM or no DM as it is expected in the population of patients with the HF in real life.

Via IRT it will be ensured that approximately a minimum of 35 % of the trial population will be patients with DM, a minimum of 15 % will be patients with pre -DM and a minimum of 20 % will be non-diabetic patients.

Additionally recruitment to the three categories of DM, pre-DM or no DM will be monitored on regional level. Capping on regional level may be applied to achieve a contribution of each region to each category of diabetes status. DM in this context is defined as active treatment with antidiabetic medication (for indication of DM) or screening HbA1c $\geq 6.5\%$ or history of DM. Pre-DM is defined as screening HbA1c $\geq 5.7\%$ and $< 6.5\%$ without the intake of antidiabetic medication (unless taken for a non-DM indication) and no history of DM, and patients with no DM is defined as screening HbA1c $< 5.7\%$ without any intake of antidiabetic medication (unless taken for a non-DM indication) and no history of DM [[R16-2261](#)].

IRT will be used to aim for a trial population consisting of approximately 35% to 50% with an LVEF $\geq 50\%$. To ensure adequate enrolment of patients the final decision on capping will be based on the recommendation from the ExSC during the recruitment period.

Screening of patients for this trial is competitive, i.e. screening for the trial will stop at all centres when a sufficient number of patients have been randomised to trial treatment. Investigators will be notified when screening is complete and will not be allowed to recruit additional patients thereafter. Patients who have completed visit 1 procedures prior to notification of the termination of recruitment will be allowed to be randomised in the trial, if they meet all eligibility criteria. Patient eligibility will be based upon a complete medical history including a physical examination and clinical laboratory tests. Judgment of the clinical relevance of a concomitant disease is at the discretion of the Investigator.

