5.1.2 Secondary endpoint(s)

The key secondary endpoints which are part of the testing strategy, are the following:

1. Occurrence of adjudicated HHF (first and recurrent),
2. eGFR (CKD-EPI)_{cr} slope of change from baseline

Other secondary endpoints (not part of confirmatory testing hierarchy on trial level) are the following:

- Time to first occurrence of chronic dialysis or renal transplant or sustained* reduction of $\geq 40\%$ eGFR (CKD-EPI)_{cr} or
 - sustained eGFR (CKD-EPI)_{cr} < 15 mL/min/1.73 m² for patients with baseline eGFR ≥ 30 mL/min/1.73 m²
 - sustained eGFR (CKD-EPI)_{cr} < 10 mL/min/1.73 m² for patients with baseline eGFR < 30 mL/min/1.73 m²

*An eGFR (CDK-EPI)_{cr} reduction is considered sustained, if it is determined by two or more consecutive post-baseline central laboratory measurements separated by at least 30 days (first to last of the consecutive eGFR values).

Chronic dialysis is defined as dialysis with a frequency of twice per week or more often for at least 90 days.

- Time to first adjudicated HHF
- Time to adjudicated CV death
- Time to all-cause mortality
- Time to onset of DM (defined as HbA1c $\geq 6.5\%$ or as diagnosed by the Investigator) in patients with pre-DM defined as no history of DM and no HbA1c ≥ 6.5 before treatment, and a pre-treatment HbA1c value of ≥ 5.7 and < 6.5
- Change from baseline in clinical summary score (HF symptoms and physical limitations domains) of the Kansas City Cardiomyopathy Questionnaire (KCCQ) at week 52
- Occurrence of all-cause hospitalisation (first and recurrent)

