7.3.1 Primary endpoint analyses

The primary endpoint will be evaluated on the randomised set using a Cox proportional hazards model with treatment, age (continuous), gender, geographical region, baseline status of DM (DM, pre-DM, no DM), LVEF (continuous) and eGFR (CKD-EPI)_{cr} at baseline (continuous) as covariates.

The time to the event of interest will be computed as (event date – randomisation date) + 1. All events observed after randomisation until completion of the planned treatment phase will be included in the analysis. Patients who do not have an event will be censored at the individual end of the planned treatment phase or the last day that the patient was known to be free of the event, whichever is earlier. The time to censoring will be computed as (individual end of the planned treatment phase or the last day known to be free of the event – randomisation date) + 1. For patients who have more than one primary endpoint event during the trial, the time to the first occurrence of the primary endpoint event will be considered for the primary analysis. Only the adjudicated and confirmed events will be used for the primary analysis.

Proprietary confidential information © 2019 Boehringer Ingelheim International GmbH or one or more of its affiliated companies

To detect any heterogeneity in the treatment effect among diabetic patients, pre-diabetic patients and non-diabetic patients, a subgroup analysis will be performed by including the diabetic status by treatment interaction term into the Cox model.

Standard subgroup analyses of the primary endpoint include geographical region, sex, BMI, LVEF, renal function, prognostic factors, age, ethnicity, race and different background therapies etc. More details will be specified in the TSAP.

A sensitivity analysis will be provided based on the TS only including any events up to 30 days after treatment discontinuation.

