7.6 RANDOMISATION

The trial will be performed as a double-blind design with respect to placebo and empagliflozin. Subjects will be randomised to the trial treatments in a 1:1 ratio. The randomisation will be stratified by the following factors:

- Geographical region (North America, Latin America, Europe, Asia, Other)
- Status of DM at screening:
 - no DM (HbA1c < 5.7% without the intake of antidiabetic medication, unless taken for a non-DM indication, and no history of DM), or
 - pre-DM (HbA1c $\geq 5.7\%$ and <6.5% without the intake of antidiabetic medication unless taken for a non-DM indication, and no history of DM), or
 - DM (HbA1c $\geq 6.5\%$ or intake of antidiabetic medication for a DM indication, or a history of DM)
- eGFR (CKD-EPI)_{cr} at screening
 - <60 mL/min/1.73 m²
 - ≥ 60 mL/min/1.73 m²
- LVEF
 - LVEF < 50%
 - LVEF $\geq 50\%$

Patients will be randomised in blocks to double-blind treatment via an IRT system. Approximately equal numbers of patients will be randomised to each treatment group. BI will arrange for the randomisation and the packaging and labelling of trial medication. The randomisation list will be generated using a validated system, which involves a pseudo-random number generator so that the resulting treatment will be both reproducible and non-predictable. The block size will be documented in the CTR. Access to the codes will be controlled and documented.

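### Section 7.3 classes a patient with no recorded diabetes history and a highest pre-treatment HbA1c of exactly 6.5 as Non-DM, although sections 3.3, 5.1.2 and 7.6 treat 6.5% or more as diabetes

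*Protocol*

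**What the plan says.** Section 7.3 of the current protocol gives three baseline groups for analysis.

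- The diabetic group is set out as "DM: any pre-treatment HbA1c above 6.5 or history of DM as entered in the eCRF on the medical history page".
- The intermediate group has a stricter wording at the boundary and requires "no history of DM and no HbA1c ≥ 6.5 before treatment and a pre-treatment HbA1c value of ≥ 5.7 and < 6.5".
- Whoever remains falls under a catch-all line, which reads "Non-DM: not meeting criteria of DM or pre-DM above".

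Three other sections set a diabetes threshold. Section 7.6 describes the randomisation stratum as "DM (HbA1c $\geq 6.5\%$ or intake of antidiabetic medication for a DM indication, or a history of DM". Section 3.3, on capping through the IRT, counts "screening HbA1c $\geq 6.5\%$ or history of DM" as DM, besides active antidiabetic treatment. Section 5.1.2 has the secondary endpoint "Time to onset of DM (defined as HbA1c $\geq 6.5\%$ or as diagnosed by the Investigator) in patients with pre-DM".

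Section 7.3.1 puts the three-level baseline status into the primary Cox model. It also says that "a subgroup analysis will be performed by including the diabetic status by treatment interaction term into the Cox model". Section 5.1.3 lists HbA1c change over time in the same three subgroups.

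The three lines in 7.3 are the same in version 1.0 of 2016 and in the 2019 revision.

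**The concern.** The DM line uses a strict inequality and the Pre-DM line uses its non-strict counterpart, so the value 6.5 belongs to neither. Because Non-DM is the residual group, the gap does not show up as missing data. The patient is assigned, without any flag, to the group furthest from the right one.

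That group carries weight. Section 2.1 argues that benefit should extend to patients without diabetes. Section 2.3 notes the lack of long-term safety data in them. Section 3.3 reserves a minimum share of the trial for them. The subgroup analysis by diabetic status is the only heterogeneity question for which 7.3.1 spells out a model term. Patients who are diabetic by the protocol's own criterion should not be counted there as non-diabetic.

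**Working it through.** **1. The rule, applied literally.** Take a patient with no recorded history, no antidiabetic medication and the same HbA1c at Visit 1 and Visit 2. The Flow Chart schedules HbA1c at both visits, and both precede the first dose.

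| HbA1c | Stratum (7.6) | Analysis group (7.3) | 7.3 with the threshold at 6.5 or more |
|---|---|---|---|
| 5.6 | no DM | Non-DM | Non-DM |
| 5.7 | pre-DM | Pre-DM | Pre-DM |
| 6.4 | pre-DM | Pre-DM | Pre-DM |
| **6.5** | **DM** | **Non-DM** | **DM** |
| 6.6 | DM | DM | DM |

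The order breaks at one point: 6.4 is Pre-DM, 6.5 is Non-DM, 6.6 is DM. With a recorded history every row is DM.

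**2. Who is affected.** All pairs of two pre-treatment values from 5.0 to 8.0 in steps of 0.1 give 31 × 31 = 961 combinations. Without history, 31 change group when the threshold is corrected. These are exactly the pairs whose maximum is 6.5, such as 6.5 and 6.0. All 31 move from Non-DM to DM.

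**3. How many patients.** The protocol states neither an HbA1c distribution nor the reporting precision, so this step rests on assumptions. Let p be the affected share of all randomised patients, and let true non-diabetics be 20% of the trial, the approximate minimum in section 3.3. The affected share of the Non-DM group is then p / (0.20 + p).

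| p | of 4126 | of 6000 | share of Non-DM |
|---|---|---|---|
| 0.5% | 21 | 30 | 0.005 / 0.205 = 2.4% |
| 1% | 41 | 60 | 0.01 / 0.21 = 4.8% |
| 2% | 83 | 120 | 0.02 / 0.22 = 9.1% |
| 3% | 124 | 180 | 0.03 / 0.23 = 13.0% |

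A simulation gives a second view. It assumes that half the patients have no history, that HbA1c is reported to 0.1, that the within-person SD is 0.12, and that there are two pre-treatment values. With mean 5.7 and SD 0.4 or 0.5 in the no-history patients, about 23% of the trial is no-DM at screening, so the 20% minimum is met. About 2.0% and 2.8% of no-history patients then have a maximum of exactly 6.5. That is 41 and 58 of 4126, or about 5% and 6% of the Non-DM group. Roughly 58% to 60% of them had 6.5 at screening and so were randomised as DM. The rest had a lower screening value.

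**4. Effect on the subgroup estimate.** For illustration, assume hazard ratios of 0.90 in true non-diabetics and 0.70 in diabetics, with events in proportion to patients. At 13% contamination the labelled Non-DM hazard ratio is about exp(0.87 × ln 0.90 + 0.13 × ln 0.70) = 0.87. The shift is 0.13 × (ln 0.90 − ln 0.70) ≈ 0.03 on the log scale. With 23% of 841 events, about 193, the standard error in that subgroup is about √(4 / 193) = 0.14.

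**The case against.** The strongest reply is that this is a slip of one word. The Pre-DM line directly below uses 6.5 or more, as do three other sections, so the intended threshold is not in doubt and a programmer would probably implement it. That bears on severity but does not remove the point. The rule is stated in full, and followed as written it gives the wrong group. An analysis plan that used the other threshold would depart from the protocol.

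Several stronger readings are tempting, and the document does not support them.

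- **That the primary result is compromised.** Diabetes status is a pre-treatment covariate, and its misclassification does not depend on the randomised arm. The type I error of the primary test is not at risk, and any change in the hazard ratio should be negligible. The interaction is a subgroup analysis outside the three-step hierarchy of section 7.2.
- **That diabetics in general are analysed as non-diabetic.** Anyone with a recorded history or any value above 6.5 is classed correctly.
- **That a fifth of the Non-DM group could be wrong.** A mean HbA1c of 6.0 (SD 0.5) in patients without history gives about 21%. It also leaves only about 12% of the trial as no-DM at screening, below the 20% minimum that section 3.3 says the IRT will ensure.
- **That the missing medication criterion is a comparable fault.** Section 7.6 includes "or intake of antidiabetic medication for a DM indication, or a history of DM" and 7.3 omits the medication part. A patient treated for diabetes would ordinarily have it in the medical history, which 7.3 does use. Nothing in the protocol suggests that many patients are lost this way.

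**Conclusion.** Section 7.3 is wrong as written at one value of HbA1c. Patients with no recorded history and a maximum of exactly 6.5 are labelled Non-DM, against the protocol's threshold everywhere else. This follows from the text alone.

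The size does not. About 2% to 13% of the Non-DM group is affected if 0.5% to 3% of the trial falls on the boundary and non-diabetics are at their 20% minimum. The simulated distributions that respect that minimum give about 5% to 6%. All of these figures assume that HbA1c is reported to one decimal. With finer reporting, exact ties at 6.5 would be rarer.

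The consequence is confined to the labelling of the diabetes subgroups, with a small blurring of the interaction contrast that is well below its sampling error. Severity is minor to should-fix. The reason to act is that an unambiguous error in a pre-specified subgroup definition costs almost nothing to remove before unblinding, and could look data-driven if corrected afterwards.

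**What to change.** In the DM line of section 7.3, replace the condition of being above 6.5 with a pre-treatment HbA1c of 6.5% or more. Leave the Pre-DM and Non-DM lines unchanged. The three groups then run in order with no gap, and nobody outside the affected set is reclassified. The cost is one line in the protocol and the same change in the derivation program, with no effect on sites or patients.

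Adding antidiabetic medication for a DM indication to the DM line is optional. If it is added, the Pre-DM line must exclude such patients too. Otherwise a medicated patient with no recorded history and an HbA1c from 5.7 to below 6.5 would meet both definitions.

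Neither change makes the analysis groups identical to the strata. Section 7.3 uses any pre-treatment value, while 7.6 uses status at screening, so a patient with 6.4 at screening and 6.6 at Visit 2 is randomised as pre-DM and analysed as DM under either wording. Using all baseline values is a legitimate choice and needs no correction.
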